## **Study Protocol**

### **Behavioral Protocol**

Performance on the pre-testing measures was used to identify candidate target sounds for the SPT protocol for each individual. Up to 3 target sounds were identified for each participant, as in previous studies with SPT (see Bailey et al., 2015). The targets sounds were single consonants or clusters tested at the word level (see Table 1). Lists of 16-20 words with the target sounds were generated and administered to participants during subsequent pre-treatment sessions. For every target sound, two lists of 8-10 words each were generated in order to have a trained and untrained item list. The trained list(s) were those items that were trained/treated using SPT during the treatment phase. For the probe trials, participants were asked to simply repeat each word in the list spoken by the SLP. At least 5 baseline probe trials were conducted prior to treatment, and performance had to fall between 50-100% errors for each target to be included in the treatment phase. This criterion ensured a sufficiently low baseline to minimize ceiling effects in the behavioral data during treatment. Also, performance on the final three probe trials prior to treatment had to fall within 15% of each other, in order to establish a stable baseline; otherwise, the baseline phase was extended until this criterion was met (see Fisher et al., 2003).

Following the pre-treatment (baseline) phase, the treatment phase consisted of the SPT protocol delivered to participants in 1-hour sessions, 3 days a week, for a total of 16 sessions over 5.5 weeks. The SPT protocol was the same as that developed and extensively studied by Wambaugh and colleagues (see Wambaugh & Nessler, 2004). Table 2 shows the SPT hierarchy, which involves verbal repetition, imitation, and articulatory placement cueing. The same list(s) of 8-10 trained items developed during the baseline phase were trained using this hierarchy throughout the 5.5 week period.

### *SPT Treatment Hierarchy*

---

**Step 1:** SLP produces target word in carrier phrase, “I say” and requests a repetition of the word in the phrase. If correct, SLP provides feedback concerning accuracy, requests 5 additional productions, and the next item is presented. If incorrect, SLP provides feedback concerning accuracy, and the next step in the hierarchy is attempted.

**Step 2:** SLP shows the target word in printed form and underlines the sound(s) produced incorrectly. SLP indicates problem sounds, produces the target word (no carrier phrase), and requests a repetition. If correct, SLP provides feedback concerning accuracy, requests 5 additional productions, and the next item is presented. If incorrect, SLP provides feedback concerning accuracy, and the next step in the hierarchy is attempted.

**Step 3:** SLP says, “Watch me, listen to me, say it with me” and produces the target word simultaneously with the participant. This procedure is attempted up to three times in the hope of eliciting a correct production. If correct, SLP provides feedback concerning accuracy, SLP requests 5 additional productions, and the next item is presented. If incorrect, SLP provides feedback concerning accuracy, and the next step in the hierarchy is attempted.

**Step 4:** SLP provides articulatory placement cues appropriate to the sound production errors and repeats the procedures in Step 3. If correct, SLP provides feedback concerning accuracy, requests 5 additional productions, and the next item is presented. If incorrect, SLP provides feedback concerning accuracy, and the next item is presented.

---

Improvement in response to the SPT protocol was measured by performance (percent correct) on the probe trials during the treatment phase. The probe trials were administered prior to the start of every other SPT session. Following the treatment phase, participants underwent post-testing with the same standard speech and language measures used during pre-treatment.

*Behavioral Data Analysis.* The primary behavioral outcome measure in the current study was SPT effect size on trained items ( $d_2$  index; Busk & Serlin, 1992). This  $d_2$  index reflects the difference in probe trial performance during pre-treatment versus the end of treatment:

$$d_2 = \frac{M_{A2} - M_{A1}}{SD_{pooled}}$$

where  $M_{A1}$  is the mean percent correct on the last five probe trials during the baseline phase prior to treatment,  $M_{A2}$  is the mean percent correct on the last three trials at the end of the treatment phase, and  $SD_{pooled}$  is the pooled standard deviation of the two phases. Effect size ( $d_2$ ) calculation reflects both magnitude of change and variability (Bloom, Fischer, & Orme, 2003; Cohen, 1988). When there was more than one target sound, the average effect size was used in the analyses relating treatment effects to plasticity changes (Beeson & Robey, 2006).

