Statistical Analysis Plan

Study Title: Brain Biomarkers of Response to Treatment for Apraxia of Speech

NCT#: 02046941

Date: 1-9-2014

Data Analysis

Behavioral Data. Treatment effect sizes for treated and untreated items were calculated separately for each sound target using the Busk and Serlin (1992) d_2 statistic. This effect size is derived by calculating the difference between the average performance from the comparison design phases (e.g., M_{A1} and M_{A2}) and dividing this difference by the pooled standard deviation of the two phases:

$$d_2 = \frac{M_{A2} - M_{A1}}{SD_{pooled}}$$

where M_{A1} was based on the final five probe trials during the baseline phase prior to treatment, and M_{A2} was based on the final three probe trials at the end of the treatment phase (consistent with prior SPT studies; Wambaugh et al. 2013). For participants who were trained on more than one target sound, the d_2 value represents the average d_2 across targets (Beeson & Robey, 2006). Based on previous SPT research (Bailey et al., 2015), the cut-off value for what was considered a large effect size for treated items was $d = 9.6$, $d = 7.0$ for a medium effect size, and $d = 5.2$ for a small effect size. The cut-off values for untreated items were $d = 6.7$ for large effect size, $d = 3.8$ for medium effect size, and $d = 2.2$ for small effect size.

MRI Data. To relate treatment effect size to lesion site, participants' normalized lesions were first visualized in MRIcron and overlaid on the automated anatomical labeling (AAL) atlas, which is based on 116 parcellations of the brain (Tzourio-Mazoyer et al., 2002). We focused on 4 regions of interest (ROIs) that have been previously implicated in AOS, SPGI, Broca's area, SMG, and pre-central gyrus. The percentage of each AAL region affected by an individual's lesion was then calculated in MRIcron. Participants' behavioral data (effect size) and individual anatomical lesion data were analyzed using a Partial Least Square (PLS) regression: Effect size was related to the lesion variables in a leave-one-out manner.

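### Does the primary effect size d2 need changing because its last three word probes precede the end of the 16 treatment sessions?

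*Protocol*

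**What the plan says.** The protocol (Behavioral Protocol) sets treatment at three sessions a week, "for a total of 16 sessions over 5.5 weeks". For each target sound, "two lists of 8-10 words each were generated in order to have a trained and untrained item list".

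Under SPT Treatment Hierarchy it fixes the probe timing: "The probe trials were administered prior to the start of every other SPT session". It does not say whether the odd or the even sessions were probed. The primary behavioural outcome is d2 on trained items. This "index reflects the difference in probe trial performance during pre-treatment versus the end of treatment". The first mean, M_A1, uses the last five baseline probes. The second, M_A2, "is the mean percent correct on the last three trials at the end of the treatment phase". The denominator is the pooled SD of the two phases, and the protocol notes that the d2 "calculation reflects both magnitude of change and variability".

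The SAP (Data Analysis, Behavioral Data) agrees that M_A2 "was based on the final three probe trials at the end of the treatment phase", and adds that this is in line with earlier studies of the treatment. It takes its cut-offs for treated items (5.2 small, 7.0 medium, 9.6 large) from that literature.

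The only testing described after treatment is this: "Following the treatment phase, participants underwent post-testing with the same standard speech and language measures used during pre-treatment".

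**The concern.** The protocol describes d2 as a contrast with the end of treatment, yet on the stated schedule every probe that enters M_A2 is followed by at least one more session. A participant who has reached a plateau loses nothing by this. A participant who is still improving loses twice: M_A2 lies below the level finally reached, and the rise across the three probes enters the pooled SD as though it were noise.

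Two people with the same level after session 16 could thus have different d2 values because one got there sooner. The SAP relates d2 to lesion load by partial least squares and to pre- to post-treatment change in FA and cortical thickness. If learning speed varies between participants, those analyses relate the brain measures to a mixture of speed and level that a reader cannot separate.

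**Working it through.** **1. Schedule (documents only).** 3 sessions a week × 5.5 weeks = 16.5, which agrees with the stated 16. A probe before every other session gives 8 probes.

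- Odd sessions probed: the last three precede sessions 11, 13 and 15, after 10, 12 and 14 completed sessions. Mean 12; 12/16 = 75%.
- Even sessions probed: the last three precede sessions 12, 14 and 16, after 11, 13 and 15 completed sessions. Mean 13; 13/16 = 81%.

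**2. Effect on d2 (assumed curves and noise).** Assume 20% correct at baseline (80% errors, within the protocol's 50-100% entry range) and 80% after session 16 for everyone. With s sessions completed and time constant tc:

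y(s) = 20 + 60 × (1 − e^(−s/tc)) / (1 − e^(−16/tc)), or y(s) = 20 + 60 × s/16 for linear improvement.

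With five baseline and three late probes there are 4 + 2 = 6 degrees of freedom. If SS is the sum of squares of the trend across the three late probes and σ the probe noise SD, then approximately

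d2 = (M_A2 − 20) / √(σ² + SS/6).

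With no trend and the final level reached, d2 = 60/σ: 12.0, 7.5 and 5.0 at σ = 5, 8 and 12.

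Worked case: tc = 8, odd sessions, σ = 8. Here M_A2 = 73.58 and SS = 30.75, so d2 = 53.58 / √(64 + 5.125) = 6.44, which is 86% of 7.5.

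| Curve | M_A2 (odd / even) | Shortfall from 80 | d2, σ = 5 | d2, σ = 8 | d2, σ = 12 |
|---|---|---|---|---|---|
| tc 4 | 77.82 / 78.55 | 2.2 / 1.5 | 11.37 / 11.59 | 7.18 / 7.29 | 4.80 / 4.87 |
| tc 8 | 73.58 / 75.44 | 6.4 / 4.6 | 9.76 / 10.30 | 6.44 / 6.72 | 4.39 / 4.56 |
| tc 12 | 71.23 / 73.64 | 8.8 / 6.4 | 8.86 / 9.46 | 6.02 / 6.36 | 4.15 / 4.36 |
| Linear | 65.00 / 68.75 | 15.0 / 11.3 | 6.80 / 7.37 | 4.95 / 5.36 | 3.53 / 3.82 |

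The SAP category can change with learning speed at several noise levels. Time constants 4 and 8 fall on different sides of a cut-off at σ = 5.5 (10.4-10.6 large, 9.0-9.5 medium), at σ = 8 (medium, small) and at σ = 10.5 (5.5-5.6 small, 5.0-5.19 below small). The planned lesion and MRI analyses use d2 itself, however, not its category.

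**3. What is known about the noise.** The protocol requires the final three baseline probes to lie within 15% of each other. The largest SD three such values can have is √(150/2) = 8.7 points (two at one end, one at the other). That bounds those three probes only. Independent-item binomial noise at 20% or 80% correct is 100 × √(0.16/10) = 12.6 points for 10 words and 100 × √(0.16/8) = 14.1 for 8. The noise level is therefore not settled by the documents. One word is worth 10 to 12.5 points.

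**4. The alternative: one word probe after session 16.** The standard error of change from the five-probe baseline is:

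- one post-treatment probe: σ × √(1/5 + 1) = 1.095σ;
- three late probes, as planned: σ × √(1/5 + 1/3) = 0.730σ;
- ratio 1.5.

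At σ = 12.6-14.1 this is 13.9-15.5 points against 9.2-10.3 for one target. Averaged over three targets (divide by √3) it is 8.0-8.9 against 5.3-6.0.

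**The case for a change.** The strongest case for a change is that the arithmetic in step 1 is certain and the possible effect is not trivial. Steady linear improvement would leave d2 at 57-61% of its no-trend value at σ = 5 and 71-76% at σ = 12. Improvement concentrated late in treatment would lose more. The measure is the primary behavioural outcome and enters every brain analysis, and repeating 16-20 words per target (at most 48-60 for three targets) at a post-testing visit already held costs a few minutes. If noise were as low as σ = 5, the single probe's standard error for one target would be about 5.5 points, smaller than some of the shortfalls above.

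The timing stands, and so does the caution that d2 describes late-treatment performance. The case for changing the plan does not. It depends on how much learning speed varies between participants, and the documents say nothing about that; a shortfall common to all participants would leave a correlation unchanged. Neither the direction nor the size of any effect on the planned correlations can be derived. Speed of learning may also be a legitimate part of treatment response, so a final-level measure would answer a different question without being clearly better. It would be noisier, could include retention or forgetting, and would have no published cut-offs. It would also add parallel analyses to a plan that says it wished to limit comparisons.

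**Conclusion.** No change is needed. The protocol and SAP define M_A2 identically, the formula follows from that definition, and what is meant by the end of treatment is spelled out where d2 is defined. Averaging three late probes is a fair trade-off: it gives up some closeness to session 16 for a standard error of change that is two thirds of the single-probe value.

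The one gap is that the probed sessions are not named. It moves the mean timing by one session (12 or 13 of 16) and M_A2 by about 0.7 to 2.4 points on the decelerating curves, or 3.75 points on the linear one. The authors can state the sessions from their records when they report, and readers should take d2 as performance late in treatment. Both documents are written in the past tense, so a further probe may in any case no longer be possible.

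The timing figures rest on the stated schedule alone, and an undocumented closing probe would move them later. The shortfalls and d2 values rest on the assumed 20% and 80% levels, curve shapes and noise SDs, none of which the documents supply.

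### Does averaging d2 over one to three target sounds, without using the number of targets, undermine the correlations with FA and cortical thickness change?

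*Protocol*

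**What the plan says.** The protocol's Behavioral Protocol section sets the number of targets per person: "Up to 3 target sounds were identified for each participant". They come from the individual's own pre-testing: "Performance on the pre-testing measures was used to identify candidate target sounds for the SPT protocol for each individual". Each target has its own word lists: "For every target sound, two lists of 8-10 words each were generated", one list trained and one not. The schedule does not depend on the number of targets. Treatment was given "in 1-hour sessions, 3 days a week, for a total of 16 sessions over 5.5 weeks", and the "trained items developed during the baseline phase were trained using this hierarchy throughout the 5.5 week period".

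The Behavioral Data Analysis text, under the SPT Treatment Hierarchy heading, makes trained-item d2 the primary behavioral outcome. It adds: "When there was more than one target sound, the average effect size was used in the analyses relating treatment effects to plasticity changes". The SAP (Data Analysis, Behavioral Data) likewise calculates d2 for each target and then averages, with a citation for the convention. The last paragraph of the SAP's MRI Data analysis reports correlation coefficients between effect size and percent change in FA and cortical thickness.

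The analysis text does not mention the number of targets, and neither document says how session time was divided between lists. The protocol refers to a Table 1 for the target sounds; that table is not in the supplied text and may list them by participant.

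**The concern.** Total practice equals the number of targets multiplied by practice per target, so no schedule can equalize both for someone with one target and someone with three. If every hour is filled, practice per target differs up to 3-fold, which could affect d2. If instead each list gets a single pass at a common pace, total practice differs up to 3-fold, which could affect brain change. In both cases the person contributes one averaged d2 to the FA and thickness correlations.

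If the number of targets influenced both d2 and brain change, it could create a correlation where none exists or hide a real one. Relating treatment response to brain change is a main purpose of the study, so this deserves a check. The lesion PLS regression is a separate matter: targets are chosen from pre-testing performance, so their number may itself follow from the lesion.

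**Working it through.** **Schedule.** Three sessions a week for 5.5 weeks gives 3 × 5.5 = 16.5 sessions, and 16 / 3 = 5.33 weeks. The stated 16 sessions over 5.5 weeks agree within rounding. Total time is 16 × 1 h = 16 h = 960 min.

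**Practice per target**, with sessions filled and time shared equally (an assumption), for k targets with 8 to 10 trained items each:

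| k | Trained items (8k to 10k) | Hours per target (16/k) | Minutes per item over treatment (960/10k to 960/8k) |
|---|---|---|---|
| 1 | 8–10 | 16 | 96–120 |
| 2 | 16–20 | 8 | 48–60 |
| 3 | 24–30 | 5.33 | 32–40 |

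The 3-fold range is correct under that assumption.

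**Could total time differ instead?** The hierarchy ends an item with "requests 5 additional productions, and the next item is presented" and has no rule for what follows the last item, so a single pass is possible on the wording. At a pace that fits three lists into 60 minutes, one list would take 60 / 3 = 20 minutes. That sits badly with one-hour sessions for everyone. The more natural reading is 16 hours for all, with practice per target as the quantity that varies.

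**What distortion needs.** If the number of targets correlates a with averaged d2 and b with brain change, it induces by itself a correlation of a × b: 0.2 × 0.2 = 0.04, 0.4 × 0.4 = 0.16, and 0 if either is 0. The documents give no value for a or b. With total time fixed, the treatment-time argument supplies a but not b.

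**Size when only d2 is affected.** The documents state no sample size, SDs or distribution of targets, so these are assumptions: targets in equal thirds; between-person SD of true response 1.5, of which a share 0.8 is linked to brain change; sampling variance of averaged d2 equal to 9/k; d2 falling by a fixed amount per extra target. The sampling SD of 3 for one target is plausible: with five baseline and three end probes, independent and normal, the SD of d2 is 2.3, 3.1 or 4.1 at true values of 5.2, 7.0 or 9.6, the SAP's cut-offs for treated items.

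- Variance of averaged d2 apart from the fall: 1.5² + 9 × (1 + 1/2 + 1/3)/3 = 2.25 + 5.5 = 7.75.
- Correlation when the number of targets plays no part: 1.5 × 0.8 / √7.75 = 1.2 / 2.784 = 0.431.
- The variance of k in equal thirds is 2/3. A fall of 0.5 adds 0.25 × 2/3 = 0.167, giving 1.2 / √7.917 = 0.426.
- A fall of 1.5 adds 2.25 × 2/3 = 1.5, giving 1.2 / √9.25 = 0.395.

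Simulation (20,000 trials per setting) agrees. Detection uses two-sided 0.05 as a yardstick, since the plan specifies no test:

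| Fall per extra target | r unadjusted | r adjusted | Detection, n 20 (unadjusted, adjusted) | Detection, n 30 (unadjusted, adjusted) |
|---|---|---|---|---|
| 0 | 0.43 | 0.43 | 50%, 48% | 69%, 67% |
| 0.5 | 0.42 | 0.42–0.43 | 49%, 48% | 68%, 67% |
| 1.5 | 0.39 | 0.42–0.43 | 42–43%, 47–48% | 60%, 67% |

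At a fall of 0.5, adjustment gains nothing. It helps visibly only at 1.5, a figure that nothing in the documents supports.

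**The case for a change.** The strongest opposing case lets the number of targets act on both variables. With no true link, a relation of 0.5 to brain change and a fall of 1.5 give a correlation of −0.18 and false positives of 12% to 16%; adjustment restores about 0 and 5%. With a true link, a relation of 0.3 and a fall of 0.5, the correlation is 0.36 unadjusted against 0.42 adjusted, with detection of 37% against 47% at n 20. The number of targets is known before treatment and d2 already exists for each target, so a check would cost little.

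Three things weaken this. First, these settings need a relation to brain change that the treatment-time argument does not provide when everyone has 16 hours; it would have to come from severity or a mixed schedule. Second, the gain with a true link depends on how the model is built. The figures above tie d2 only to the part of brain change unrelated to the number of targets, which favors adjustment. If d2 is tied to all of brain change, the same setting gives 0.39 against 0.41, with detection of 42% against 45% at n 20. With no fall, adjustment loses: 0.42 against 0.41, and 50% against 45%. A fall of 1.5 still shows a clear gap, 0.29 against 0.41, but on an assumption without support.

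Third, the number of targets may mark severity. If severity drives brain change, brain change drives d2 and the number of targets only reflects severity, adjustment lowers a genuine 0.43 to between 0.42 and 0.39. If severity causes both with no direct link, it moves 0.16 to 0.11, or 0.27 to 0.18. An adjusted result therefore could not be read as an effect of practice.

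What stands is the reporting point: the supplied analysis text does not provide for showing the number of targets. The division of session time can be reported only if it was recorded, which neither document says.

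**Conclusion.** No change to the plan is needed. The arithmetic is right: practice per target could differ 3-fold (16, 8 or 5.3 hours) if sessions were filled and shared equally. It does not follow that the correlations are distorted. That needs the number of targets to be related to both d2 and brain change, and neither relation is documented. On the natural reading of the schedule only d2 is exposed, and the loss runs from nothing measurable (0.42 against 0.42 to 0.43) to 0.39 against 0.43, under assumed sample sizes, SDs and falls.

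Averaging d2 across targets is openly stated and cited in both documents. Whether to adjust for a count that may mark severity or follow from the lesion is a trade-off on which competent statisticians would differ, and no planned claim would depend on the adjusted figure. A table of the number of targets, with mean d2 by number, would be a sensible courtesy to readers and can be added when reporting without amending the plan. An adjusted correlation, if shown at all, should be labelled exploratory.

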### **MRI Protocol**

Our MRI imaging protocol is consistent with the imaging parameters described in the NIH CDEs for MRI Trauma Protocol for 3T-Tier 1. Brain imaging data was acquired on a new Siemens Magnetom Verio open-bore 3T MRI scanner with 12-channel parallel imaging capabilities. With its wide and short bore, this scanner has been designed to optimize patient comfort. We acquired high-resolution structural scans using a 3D T1w MPRAGE (magnetization-prepared rapid gradient echo) protocol with 1 mm^3 isotropic resolution (TR/TE/TI = 2400 / 3.16 / 1000 ms, flip angle = 8°; FOV = 256 mm; imaging matrix = 256 x 256;

acquisition time = 4.5 minutes). Two T1w images were acquired and averaged to improve the contrast-to-noise ratio. FLAIR and fast spin echo T2-weighted images were also acquired with the default Siemens pulse sequences for the visual assessment of brain lesions.

High angular resolution diffusion imaging (HARDI) data were acquired with a high diffusion weighting ( $b$  factor = 2000 s/mm $^2$ ) and 64 gradient (40 mT/m) encoding vectors, uniformly distributed on a sphere. These parameters maximize diffusion sensitivity and angular contrast while attaining clinically feasible acquisition times ([Jones et al., 2002](#)). Parallel imaging (iPAT, Siemens) with GRAPPA (generalized auto-calibrating partially parallel acquisition) was employed to reduce echo train length and echo time (TE) in the DW-MRI measurements, and to reduce the susceptibility-induced EPI geometric distortions and to improve the signal-to-noise ratio (SNR). 8 non-diffusion weighted ( $B_0$ ,  $b$  = 0 s/mm $^2$ ) images were also acquired, one before each group of 8 diffusion weighted images. Other HARDI acquisition parameters are: Twice-refocused spin-echo (TRSE) echo-planar imaging (EPI); 2 mm $^3$  isotropic voxel resolution; TR/TE = 15,500/93 ms; Bandwidth = 1817 Hz; 65 axial slices in the inter-commissural plane (interleaved, no gap) for whole-cerebral coverage; Flip angle = 90°; Field of view (FOV) = 240 cm; Imaging matrix = 120 x 120; GRAPPA acceleration factor = 2; 6/8 phase partial Fourier (PPF) sampling. The bipolar (twice-refocused) diffusion gradients implemented on Siemens VB17 are designed to minimize eddy current effects. In order to minimize the effects of brain pulsations, cardiac gating were applied to trigger image acquisition at the beginning of the R-R cardiac cycle. Total acquisition time was 19-20 minutes. A field map was also acquired with the same slice prescription as the HARDI images for off-line EPI geometric distortion correction.

Fiber pathways were traced using the streamline tractography technique (Wakana, et al., 2007; Wedeen, et al., 2008). Whole-brain tractography approach was used to trace fibers from seed points in all white matter voxels using the Fiber Assignment by Continuous Tracking (FACT) algorithm (Mori, et al., 1999) implemented in TrackVis. For DTI data, FACT find the best matching fiber trajectory that is consistent with the orientations of voxel-wise principle diffusion direction vectors identified from the diffusion tensor. Multiple diffusion direction vectors are possible at each voxel, depending on the orientation distributions determined by the high-angular resolution measurements (Schmahmann, et al., 2007; Wedeen, et al., 2005, 2008). This allows crossing-fibers to be resolved and fibers to be traced towards their cortical origins and terminations. Stopping criteria for fiber tracing were an angle threshold of 45° and FA threshold of 0.15. While FA thresholds of 0.2 or higher are more commonly used (Mori et al., 2001), FA values are

lower in stroke patients (Ciccarelli, Catani, Johansen-Berg, Clark, & Thompson, 2008), so that a lower threshold is more appropriate. White matter segmentations obtained from T1 anatomical images was used to mask out regions where tractography might provide erroneous results. Fibers shorter than 50 mm and longer than 200 mm were also excluded to reduce false positives (i.e., artifactual/spurious fibers).
